#### 4. SUBJECT REGISTRATION

All subjects must be registered through the Big Ten Cancer Research Consortium (BTCRC) Administrative Headquarters' (AHQ) electronic data capture (EDC) system OnCore®. A subject is considered registered when an 'On Study' date is entered into OnCore®.

Subjects must be registered after signing consent but prior to starting protocol therapy. Protocol therapy must begin therapy within 5 business days of registration.

# **Subjects Who Do Not Begin Study Treatment**

If subject signs consent, is registered to the study, and later is not able to begin the planned study treatment, for whatever reason, the subject will be removed from study and treated at the physician's discretion. The subject will be considered a screen/baseline failure and be replaced. The reason for removal from study will be clearly indicated in EDC system.

If a subject begins treatment, and then is discontinued for whatever reason, the subject must be followed per section 7.5.

#### 5. TREATMENT PLAN

## 5.1. Overall Design and Study Plan

This is a non-randomized, open-label, single-arm, multicenter, phase II study of palbociclib in combination with tamoxifen in subjects with HR(+)/HER2(-) advanced breast cancer who have not received prior systemic anti-cancer therapies for their advanced/metastatic disease. The primary objective of the Phase II trial is to determine progression free survival (PFS) based on RECIST 1.1 Treatment will continue until disease progression, unacceptable toxicity, subject refusal, or subject death either from progression of disease, the therapy itself, or from other causes. Subjects, who voluntarily stop the study, have progressive disease, or unacceptable toxicities will be followed for a total of 24 months after discontinuation of study drug.

If funding is secured, correlative research analyses includes correlating alterations in circulating tumor DNA at the time of progression, correlating molecular alterations of genes associated with ER+ breast cancer in tumor tissue samples with clinical outcome and at the time of progression, comparing difference in response for subjects presenting with de novo metastatic breast cancer to subjects that progressed while on aromatase inhibitors, and comparing differences in response and toxicity profile in African American and Hispanic subjects to Caucasian subjects.

#### **5.2.** Pre-medication

Pre-medication is not required but may be administered per physician discretion.

# 5.3. Drug Administration

#### 5.3.1. Palbociclib + Tamoxifen Administration

The palbociclib dose will be 125 mg administered orally once daily on days 1-21 of each 28-day cycle. Subjects will not take palbociclib on days 22-28. The tamoxifen dose will be 20 mg administered orally once daily for every day of the 28-day cycle (i.e., continuously). It is encouraged but not mandatory that premenopausal subjects will also receive treatment with Goserelin or equivalent (e.g. Lupron) given as an injectable subcutaneous implant on day 1 of every 28 days cycle or every 3 months.

Drug	Dose	Route	Schedule	Cycle Length
Palbociclib	125mg	Oral	Days 1-21	20 days
Tamoxifen	20mg	Oral	Continuous	28 days

Palbociclib should be taken with food in combination with Tamoxifen. Subjects should be encouraged to take their dose at approximately the same time each day.

#### 5.3.2. Missed Doses:

Missed doses may be taken up to 6 hours of the time that the dose was scheduled. If the timing is beyond 6 hours, the subject will skip the dose and take the next dose as scheduled.

If emesis occurs after study medication ingestion and whole capsule(s) are visible in the vomitus, replacement capsule(s) should be taken; otherwise, the dose will not be re-administered and subjects should simply adhere to the dosing schedule and resume dosing at the next scheduled time with the prescribed dosage. Subjects should record the time of the emesis in their dosing diary (see Documents/Info tab of the EDC). Under no circumstance should a subject repeat a dose or double-up doses.

# **5.4.** Supportive Care

Optimal patient care is to be given to all subjects.

Subjects should receive full supportive care during the study, including transfusion of blood and blood products, treatment with antibiotics, analgesics, erythropoietin, or bisphosphonates (or denosumab), when appropriate.

Subjects should receive appropriate supportive care measures as deemed necessary by the treating investigator including but not limited to the items outlined below:

- Nausea/vomiting: Nausea and vomiting should be treated aggressively, and consideration should be given in subsequent cycles to the administration of prophylactic antiemetic therapy according to standard institutional practice. If prophylactic antiemetic therapy is needed, 5-HT3 receptor antagonists (without corticosteroids) should be tried first. Due to the potential of benzodiazepines to cause sedation, the use of benzodiazepines for antiemetic prophylaxis should be reserved for subjects who cannot be satisfactorily managed otherwise. Subjects should be strongly encouraged to maintain liberal oral fluid intake.
- Anti-infectives: Subjects with a documented infectious complication should receive oral or IV antibiotics or other anti-infective agents as considered appropriate by the treating investigator for a given infectious condition, according to standard institutional practice.

• Prophylactic myeloid growth factors are not permitted for prevention of neutropenia and are only permitted if clinically indicated in response to a clinically significant episode of neutropenia.

#### 5.5. Concomitant Medications

Medications specifically prohibited in the exclusion criteria are not allowed during the ongoing trial. If there is a clinical indication for one of these or other medications specifically prohibited during the trial, discontinuation from trial therapy may be required. The site investigator should discuss any questions regarding this with the sponsor-investigator by contacting the BTCRC Project Manager. The final decision on any supportive therapy rests with the investigator and/or the subject's primary physician. However, the decision to continue the subject on trial therapy requires the mutual agreement of the local Investigator, the sponsor-investigator, and the subject.

## **Permitted Concomitant Medications and Procedures**

All treatments the investigator considers necessary for a subject's welfare may be administered at the discretion of the investigator in keeping with the community standards of medical care. All concomitant medications will be recorded on the electronic case report form (eCRF).

Palliative radiation is permitted but palbociclib must be withheld throughout the course of radiotherapy. Palliative RT should not be delivered to a target lesion and it should not encompass more than 25% of the irradiated bone marrow. The reason for radiotherapy must be clearly documented and progression as per RECIST 1.1 must be ruled out. No dose modification of study treatment is mandated after completion palliative radiotherapy.

If elective surgery is needed during study, it is recommended the surgery be scheduled between treatment cycles. Palbociclib should be withheld 14 days prior to surgery. The next cycle of treatment may be delayed up to 4 weeks to allow for additional recovery at the discretion of the investigator.

All concomitant medications received within 28 days before the first dose of trial treatment and 30 days after the last dose of study drug should be recorded. Concomitant medications administered beyond 30 days after the last dose of trial treatment should be recorded for SAEs as defined in Section 11.

Antiemetic agents may be administered at the discretion of the investigator but are not commonly required as a prophylactic agent. All other manifestations of the subject's malignancy should be treated at the discretion of the investigator.

All other medical conditions should be treated at the discretion of the investigator in accordance with local community standards of medical care.

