#### 3.1. Inclusion Criteria

Subjects must meet all of the following applicable inclusion criteria to participate in this study:

**3.1.1** Male or female  $\geq$  18 years of age at time of consent.

**NOTE**: Both pre- and post-menopausal women are eligible.

Pre-menopausal status is defined as either:

- -Last menstrual period within the last 12 months
- -In case of therapy-induced amenorrhea, plasma estradiol and /or FSH is in the premenopausal range per local normal range.
- **3.1.2** Locally advanced, locoregionally recurrent, or metastatic disease, not amenable to curative therapy. **NOTE**: Although not required as a protocol procedure, a patient with a new metastatic lesion should be considered for biopsy whenever possible to reassess ER/PR/HER2 status if clinically indicated. If a biopsy is prospectively done as part of standard of care, the study would like to store samples for correlative research.
- **3.1.3** Histologically and/or cytologically confirmed diagnosis of ER positive and/or PR positive (ER >1%, PR >1%), HER2 negative breast cancer.

**NOTE**: Subject has HER2-negative breast cancer (based on most recently analyzed biopsy) is defined as a negative in situ hybridization test or an IHC status of 0, 1+ or 2+. If IHC is 2+, a negative in situ hybridization (e.g. FISH, CISH, SISH, DISH, etc.) test is required by local laboratory testing.

**3.1.4** Metastatic disease evaluable on imaging studies. Subjects may have measurable disease as per RECIST 1.1 or bone-only disease.

**NOTE**: Bone-only subjects are eligible if their disease can be documented/ evaluated by bone scans, CT or MRI. Their disease will be assessed using MDA criteria.

**NOTE**: Previously irradiated lesions are eligible as a target lesion only if there is documented progression of the lesion after irradiation.

**3.1.5** No prior systemic anti-cancer therapy for advanced HR+ disease.

**NOTE**: Subjects receiving adjuvant treatment with aromatase inhibitors at time of recurrence are allowed to participate. There is no AI washout period required.

- **3.1.6** Eastern Cooperative Oncology Group (ECOG) Performance Status 0-2
- **3.1.7** Adequate hepatic function within 14 days prior to registration for protocol therapy defined as meeting **all** of the following criteria:
  - aspartate aminotransferase (AST)  $\leq$  2.5 × ULN or  $\leq$  5 × ULN for subjects with known hepatic metastases and

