## 8. CRITERIA FOR DISEASE EVALUATION

Response assessments for subjects with visceral/visceral plus bone disease will be made using RECIST v1.1. Response assessments for subjects with bone only disease will be made using MDA criteria.

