# 8.1. Definitions Associated with Response Evaluation Criteria in Solid Tumors (RECIST) version 1.1

- **8.1.1. Measurable disease:** The presence of at least one measurable lesion. If the measurable disease is restricted to a solitary lesion, its neoplastic nature should be confirmed by cytology/histology.
- **8.1.1.1.** *Measurable lesions:* Measurable lesions are defined as those that can be accurately measured in at least one dimension (longest diameter to be recorded) as ≥20 mm by chest x-ray, as ≥10 mm with CT scan, or ≥10 mm with calipers by clinical exam. All tumor measurements must be recorded in millimeters (or decimal fractions of centimeters).
- **8.1.1.2.** *Non-measurable lesions:* All other lesions (or sites of disease), including small lesions (longest diameter <10 mm or pathological lymph nodes with ≥ 10 to <15 mm short axis), are considered non-measurable disease. Bone lesions, leptomeningeal disease, ascites, pleural/pericardial effusions, lymphangitis cutis/pulmonitis, inflammatory breast disease, and abdominal masses (not followed by CT or MRI), are considered as non-measurable.

Note: Cystic lesions that meet the criteria for radiographically defined simple cysts should not be considered as malignant lesions (neither measurable nor non-measurable) since they are, by definition, simple cysts.

'Cystic lesions' thought to represent cystic metastases can be considered as measurable lesions, if they meet the definition of measurability described above. However, if non-cystic lesions are present in the same subject, these are preferred for selection as target lesions.

**8.1.1.3.** *Malignant lymph nodes*. To be considered pathologically enlarged and measurable, a lymph node must be ≥15 mm in short axis when assessed by CT scan (CT scan slice thickness recommended to be no greater than 5 mm). At baseline and in follow-up, only the short axis will be measured and followed.

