# 8.1.1.4. Baseline documentation of "Target" and "Non-Target" lesions:

Target lesions. All measurable lesions up to a maximum of 2 lesions per organ and 5 lesions in total, representative of all involved organs, should be identified as target lesions and recorded and measured at baseline. Target lesions should be selected on the basis of their size (lesions with the longest diameter), be representative of all involved organs, but in addition should be those that lend themselves to reproducible repeated measurements. It may be the case that, on occasion, the largest lesion does not lend itself to reproducible measurement in which circumstance the next largest lesion which can be measured reproducibly should be selected. A sum of the diameters (longest for non-nodal lesions, short axis for nodal lesions) for all target lesions will be calculated and reported as the baseline sum diameters. If lymph nodes are to be included in the sum, then only the short axis is added into the sum. The baseline sum diameters will be used as reference to further characterize any objective tumor regression in the measurable dimension of the disease.

**Non-target lesions**. All other lesions (or sites of disease) including any measurable lesions over and above the 5 target lesions should be identified as **non-target lesions** and should also be recorded at baseline. Measurements of these lesions are not required, but the presence, absence, or in rare cases unequivocal progression of each should be noted throughout follow-up.

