## 8.4.5. Objective response rate:

The objective response rate is the proportion of all subjects with confirmed PR or CR according to RECIST v1.1 from the start of treatment until disease progression/recurrence (taking as reference for progressive disease the smallest measurements recorded since the start of treatment).

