# 8.6. Response Criteria for MD Anderson (MDA) Criteria (21)

Complete Response (CR)	Complete sclerotic fill-in of lytic lesions on XR or CT
	Normalization of bone density on XR or CT
	Normalization of signal intensity on MRI
	Normalization of tracer uptake on SS
Partial Response (PR)	Development of a sclerotic rim or partial sclerotic fill-in of lytic lesions on XR or CT
	Osteoblastic flare - Interval visualization of lesions with sclerotic rims or new sclerotic lesions in the setting of other signs of PR and absence of progressive bony disease
	• ≥ 50% decrease in measurable lesions on XR, CT, or MRI
	• ≥ 50% subjective decrease in the size of ill-defined lesions on XR, CT, or MRI
	• $\geq 50\%$ subjective decrease in tracer uptake on SS
Progressive Disease (PD)	• > 25% increase in size of measurable lesions on XR, CT, or MRI
	• > 25% subjective increase in the size of ill-defined lesions on XR, CT, or MRI
	• > 25% subjective increase in tracer uptake on SS
	New bone metastases
Stable Disease (SD)	No change
	• < 25% increase or < 50% decrease in size of measurable
	lesions
	• < 25% subjective increase or < 50% subjective decrease in size of ill-defined lesions
	No new bone metastases
	y; CT: computed tomography; SS: skeletal scintigraphy; MRI:
magnetic resonance imaging.	

Measurements are based on the sum of a perpendicular, bi-dimensional measurement of the greatest diameters of each individual lesion.

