### 12.5. Analysis of Secondary Endpoints

Characterize safety and tolerability of palbociclib and tamoxifen in first line therapy for subjects with HR(+)/HER2(-) advanced breast cancer who have not received prior systemic anti-cancer therapies for their advanced/metastatic disease.

 Proportion of subjects with each grade of adverse events as defined by CTCAE v4 will be computed along with 95% confidence intervals, and reported in a tabular and descriptive manner.

Assess response rate based on RECIST 1.1 or MDA Criteria. The response rate (complete or partial response) and 95% confidence interval for the response rate will be computed using PROC FREQ in SAS (Cary, NC).

Evaluate clinical benefit rate RR (complete, partial response, or stable disease) based on RECIST 1.1 or MDA Criteria in subjects with HR(+)/HER2(-) advanced breast cancer who have not received prior systemic anti-cancer therapies for their advanced/metastatic disease treated with palbociclib in combination with tamoxifen.

• Clinical benefit rate (complete, partial response, or stable disease) will be assessed every 8 weeks +/- 1 week while on study treatment using RECIST 1.1 (section 8) or MDA Criteria (for patients with bone only disease). Response will be recorded as disease control rate (DCR), or stable disease plus partial response plus complete response, and reported via waterfall plot. The response rate and 95% confidence interval for the response rate will be computed using PROC FREQ in SAS (Cary, NC).

Measure 2-year overall survival (OS) in subjects with HR(+)/HER2(-) advanced breast cancer who have not received prior systemic anti-cancer therapies for their advanced/metastatic disease treated with palbociclib in combination with tamoxifen.

Median OS times will be computed, and OS rate will be calculated with associated 95% confidence intervals. Kaplan-Meier curves will be plotted. Data will be analyzed using the PROC FREQ and PROC LIFETEST in SAS.

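### The limits on palliative radiotherapy in 5.5 leave irradiated bone lesions scorable under the MDA criteria, and the marrow limit cannot be applied as worded

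*Combined protocol and SAP*

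**What the plan says.** Section 5.5 (Permitted Concomitant Medications and Procedures) allows palliative radiotherapy while palbociclib is held. It asks for the reason to be documented and for RECIST 1.1 progression to be excluded. It then sets two limits in one sentence: "Palliative RT should not be delivered to a target lesion and it should not encompass more than 25% of the irradiated bone marrow".

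Section 8.1.1.4 says how target lesions are chosen: "All measurable lesions up to a maximum of 2 lesions per organ and 5 lesions in total". Section 8.1.1.2 lists what is not measurable, and the list begins "Bone lesions, leptomeningeal disease, ascites, pleural/pericardial effusions".

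Bone-only subjects are eligible (3.1.4). For them, section 8 says "Response assessments for subjects with bone only disease will be made using MDA criteria". The MDA table in 8.6 counts as partial response, among other findings, "Development of a sclerotic rim or partial sclerotic fill-in of lytic lesions on XR or CT". A fall of at least 50% in lesion size or in tracer uptake also counts. A rise of more than 25% in either is progression.

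The one rule on irradiated lesions is an entry rule in 3.1.4: "Previously irradiated lesions are eligible as a target lesion", and then only after documented progression since the irradiation.

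For the analysis, 12.5 says "Assess response rate based on RECIST 1.1 or MDA Criteria", with a 95% confidence interval.

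**The concern.** The bar on irradiating a target lesion is the only provision in 5.5 that keeps local radiotherapy effects out of later response scoring. It uses a term that, as the protocol defines it, does not reach bone. Bone is a site where palliative radiotherapy may well be wanted, and bone-only subjects are assessed on nothing else. If a lytic lesion is irradiated and then fills in, the site has a finding that the MDA table calls partial response and no instruction to set it aside. The pooled response rate could then include an effect of radiotherapy.

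The second half of the same sentence is a safety limit. Section 10.1 reports neutrophil decreases of grade 3 or worse in 66% of palbociclib-treated patients in each of two studies, so the amount of marrow in a radiotherapy field matters. A limit that a site cannot compute gives no protection.

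**Working it through.** The plan gives no figure on this point, so there is none to reproduce. The check is a comparison of text, followed by a calculation for scale.

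**Step 1. Does the bar reach bone lesions?**
- 5.5 bars radiotherapy to target lesions.
- 8.1.1.4 draws target lesions from measurable lesions.
- 8.1.1.2 puts bone lesions among the non-measurable ones, without exception.
- So, on the printed definitions, a bone-only subject has no target lesion and the bar protects none of that subject's lesions.

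**Step 2. Does anything else exclude the irradiated lesion?**
- The 3.1.4 note concerns radiotherapy before entry, not on study.
- The check in 5.5 before radiotherapy concerns progression, not later response, and names RECIST 1.1 only.
- The repeat whole-body bone scan (section 7 footnotes, 7.3, 7.4) shows other lesions and new metastases. It does not remove the irradiated lesion from scoring.
- Dedicated bone x-ray, CT or MRI is directed to the largest bone lesion (footnote 10, 7.3, 7.4). If that lesion is the one irradiated, the structural reading is taken on treated bone.
- The confirmation rule in 8.4.2 sits under RECIST. Even if it were carried over to MDA, it would re-read the same lesion.
- 8.6 as printed has no entry for a lesion irradiated on study.

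**Step 3. Which endpoint is affected?** PFS is assessed by RECIST 1.1 (2.1.1, 8.4.6, 12.4). The response rate in 12.5 takes RECIST and MDA responders together, so the effect falls there.

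**Step 4. Scale.** Shift in response rate = misclassified subjects / denominator. Section 12.5 states no denominator, so both values below are assumptions: all 48 subjects (12.3), or 40 evaluable. The number of misclassified subjects is also assumed.

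| Misclassified | Denominator 48 | Denominator 40 |
|---|---|---|
| 1 | 1/48 = 2.1 points | 1/40 = 2.5 points |
| 2 | 2/48 = 4.2 points | 2/40 = 5.0 points |
| 3 | 3/48 = 6.3 points | 3/40 = 7.5 points |

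For comparison, exact (Clopper-Pearson) 95% intervals with 48 subjects, starting from an assumed 14 responders:

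| Responders | Rate | 95% CI |
|---|---|---|
| 14/48 | 29.2% | 17.0 to 44.1% |
| 15/48 | 31.3% | 18.7 to 46.3% |
| 17/48 | 35.4% | 22.2 to 50.5% |

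The first interval is 44.1 - 17.0 = 27.1 points wide. Three false responders move the estimate by 6.3 points, less than a quarter of that width.

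**Step 5. Marrow limit.** Read literally, the share is marrow in the field divided by marrow irradiated. These are the same quantity, so the share is 100% for every field, against a limit of 25%. No field can meet it.

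**The case against.** The strongest reply is that 'target lesion' in 5.5 need not carry its RECIST meaning for subjects whom section 8 assigns to MDA. The MDA table itself speaks of measurable lesions on x-ray, CT or MRI, and in 3.1.4 the note on irradiated target lesions directly follows the bone-only note. A site could read 5.5 as barring radiotherapy to whichever bone lesion it follows. That reading is possible, but no section states it. With local assessment at several centres, it may not be applied uniformly.

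Four further objections stand in whole or in part:
- **Direction.** A reader might infer that the bias can only run upward. The documents do not support that. That radiotherapy produces sclerosis is a clinical assumption they do not state, and 8.6 also allows progression from increased uptake or size. A false response is the more plausible error, not the only one.
- **Denominator.** A reader might take it from 8.4.5, which says "The objective response rate is the proportion of all subjects with confirmed PR or CR". That definition is expressly for RECIST 1.1 and does not govern the pooled rate in 12.5. Section 12.2 lists an Evaluable set without assigning it to this analysis.
- **Source.** 8.6 summarises a cited publication. Whether that source deals with irradiated bone cannot be checked here; only the protocol's silence can be shown.
- **Rarity.** The problem needs a bone-only subject, radiotherapy without progression, treatment of a lesion that drives the score, and no progression elsewhere in bone.

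The marrow wording is probably a drafting slip, and the intent to cap the share of marrow in the field is evident. The palbociclib hold and the blood-count rules in 6.1 soften the risk. They do not make the limit measurable.

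**Conclusion.** The point holds and is minor. As printed, 5.5 and 8.6 together let a bone lesion irradiated on study go on contributing to MDA response. Each subject misclassified as a responder moves the response rate by about 2.1 points with 48 as denominator, or 2.5 with 40. Both denominators are assumptions. The documents give neither the number of bone-only subjects nor the frequency of palliative radiotherapy, so the total effect cannot be estimated. The response rate is secondary and has no test or threshold attached.

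A reader might infer that the primary result is compromised. The documents do not support that: PFS is defined by RECIST 1.1 and the sample size in 12.3 rests on PFS. No effect on the clinical benefit rate is claimed either.

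The circular marrow limit is a separate wording fault in a safety rule. It neither strengthens nor depends on the first part.

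**What to change.** **(a) In 8.6, add:** 'A bone lesion irradiated on study is not evaluable for CR or PR from the start of radiotherapy. Later MDA response is assigned from the non-irradiated lesions, with the baseline sum recalculated without the irradiated lesion and using the scheduled bone scan and CT/MRI. A response documented and confirmed before radiotherapy stands. New or progressing non-irradiated lesions count as PD.'

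The rule needs the recalculated baseline because the MDA measurement is a sum over lesions. It has to name the scheduled imaging because dedicated bone imaging is directed only to the largest lesion.

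**(b) In 5.5,** change the denominator of the marrow limit so that it reads '25% of the total bone marrow'. The RECIST 1.1 progression check stays as it is.

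**Cost.** A short added rule and one changed phrase, with no imaging beyond the schedule. The response rate may be slightly lower, and a subject whose only lesion is irradiated cannot become a responder afterwards.
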